1.3 Primary and Secondary Outcomes

The primary outcome is glycemic control. Glycemic control is difficult to accurately assess whenever antihyperglycemic medications doses change, as changing doses can mask improvements in standard glycemic outcomes. Therefore, we define an individual has having an improvement in glycemic control if s/he needs a lower dose of antihyperglycemic medications (if medication doses change) or has lower mean glucose levels (if medication doses do not change). We will use the following hierarchy of glycemic outcomes:

- 1. Achieving non-diabetic glycemia without antihyperglycemic medications (assessed as a binary outcome and analogous to T2D remission without the 3-month requirement);
- Total dosage of antihyperglycemic medications, as measured by the medication effect score (MES);
- 3. Mean glucose during a three-hour OGTT; and
- 4. Mean 24-hour glucose as measured by continuous glucose monitoring (CGM), adjusted for any changes in medication doses via the MES (see Section 4.5).

We decided to use mean 24-hour glucose as measured by CGM in lieu of HbA1c because CGM more accurately assesses the present glycemic status over the previous week, whereas HbA1c is a lagging indicator of glycemic control. The hierarchy implies that a positive or negative outcome in an upper level will always supersede any findings from lower levels in the hierarchy. In particular, if glucose-lowering medication dosages change, then assessments 1 and

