2 will supersede assessments 3 and 4 since changes in glucose-lowering medications confound the interpretation of glycemic data. If there are no changes in glucose-lowering medications, then we will use assessments 3 and 4 to determine whether there are changes in glycemic control. We will interpret the data from assessments 3 and 4 as follows. We will interpret assessment 3 (OGTT) to indicate whether the intervention improves or exacerbates glucose intolerance and underlying defects in glucose metabolism. If there is no change in assessments 1-3, we will interpret assessment 4 (CGM) to reflect only acute changes in the glycemic load and macronutrient composition of the diet. For instance, the intervention may increase mean 24-hour glucose levels in a participant who eats a low-carbohydrate diet at baseline, but this increase may simply reflect switching to a higher carbohydrate diet, not a worsening of glucose metabolism.¹ As another example, the intervention may decrease mean 24-hour glucose levels in a participant who eats a higher glycemic load diet at baseline, but this decrease may reflect switching to a lower glycemic load diet, not an improvement in glucose metabolism per se.

The secondary outcomes are liver fat, pancreatic fat, cardiovascular risk factors, and ancillary measures of glucose metabolism:

- Liver fat, as measured by magnetic resonance imaging and spectroscopy (MRI/S);
- Pancreatic fat, as measured by MRI/S;
- Insulin secretion, as measured by the oral minimal model;
- Insulin sensitivity, as measured by the oral minimal model;
- Mean insulin and C-peptide levels during the OGTT;
- Time-in-range metrics from CGM;
- Mean amplitude of glycemic excursions from CGM;
- HbA1c;

- Fasting glucose;
- Blood pressure;
- Heart rate; and
- Lipids (total cholesterol, LDL cholesterol, HDL cholesterol, and triglycerides).

Additional outcomes include body composition (subcutaneous abdominal fat, visceral fat, and waist circumference), preferences for and sensitivity to sweet tastes, diet satisfaction, food cravings, eating behaviors, mood, quality of life, and depression.

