4.3 Power Calculation

As this is a pilot and feasibility trial, the sample size was not based on a power calculation. We selected a sample size of 16 completers to provide sufficient data to inform the design of a future trial. Nonetheless, our study has 81% power to detect an 18.0% rate of attaining non-diabetic glycemia vs. a spontaneous remission rate of 0.7%.²³ Further, 16 completers provides 80% power to detect effect sizes of Cohen's d ≥ 0.78 , using a two-tailed paired t-test with α =0.05. This corresponds to a large effect size, which we expect, as participants eat a very large amount of fruit. We acknowledge that we are not powered to detect medium or small effect sizes, which may also be clinically relevant.

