4.4 Statistical Analyses

All statistical tests will be two-sided with a Type I error rate of α =0.05. Because this is a controlled-feeding trial—designed to determine the cardiometabolic effects under conditions of nearly perfect adherence—we will analyze the data per protocol in completers only. The primary comparison will be between weeks 0 and 12, with secondary comparisons between weeks 0 and 4 and between weeks 4 and 12. Data may be Winsorized if there are outliers with an overwhelming degree of influence or values that are non-physiologic . We will test whether a fruit-rich diet can induce non-diabetic glycemia without hyperglycemia medications by testing whether our observed "remission" rate differs from the spontaneous T2D remission rate of

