0.07% using an exact binomial test.²³ If there is one or more cases of non-diabetic glycemia, then the true rate is non-zero, and we will report a 95% confidence interval derived from bootstrapping. All other data will be analyzed as change scores. For all continuous data and Likert score data with at least four levels and sufficient variability, we will use linear mixed models with time as either a linear or categorical effect and with a random intercept for participants. For other data types, we will use distribution-appropriate generalized linear mixed models. Alternatively, if spline models are more parsimonious than treating time as a linear or categorical effect, we will use generalized-additive models with penalized adaptive regression splines instead. To analyze the data from CGM, we will perform a trajectory analysis to determine whether there are different "response phenotypes." Since it is conceivable that participants starting from very different baseline diets may have distinct trajectories early on, we may also consider a trajectory analysis of the data with special attention to the Ramp-Up phase and restrict the models to the Main Phase period after the trajectories converge. We will consider adjusting for covariates such as baseline values or mean 24-hour glucose levels only if statistically and clinically merited. For the inferential statistics on continuous variables, we will test for differences using least squares means evaluated at study timepoints, or alternatively, if time is most appropriately treated as a categorical variable, by the significance of the coefficient for each timepoint. We will analyze change in categorical variables using McNemar's test for dichotomous variables and Bowker's test of symmetry for variables with more categories. Finally, to assess inter-individual responses in the vein of precision nutrition, we will also report the percentages of participants who experience an improvement, no change, and a worsening in glycemic control.

5. Protocol Amendments

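### The glycemic hierarchy in Section 1.3 does not say whether an upper level overrides lower ones within a participant or for the trial, and Section 4.4 does not settle it

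*Combined protocol and SAP*

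**What the plan says.** Section 1.3 makes glycemic control the primary outcome and orders four measures: non-diabetic glycemia off medication, medication effect score (MES), OGTT mean glucose, and MES-adjusted CGM mean glucose. The ordering rule is "The hierarchy implies that a positive or negative outcome in an upper level will always supersede any findings from lower levels in the hierarchy". When doses change, assessments 1 and "2 will supersede assessments 3 and 4 since changes in glucose-lowering medications confound the interpretation of glycemic data". A positive or negative outcome is not defined for any level, and the unit of the rule is not stated.

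The surrounding text leans towards the individual. Before the hierarchy it says "we define an individual has having an improvement in glycemic control if s/he needs a lower dose of antihyperglycemic medications", or has lower mean glucose when doses stay the same. One worked example is that "the intervention may increase mean 24-hour glucose levels in a participant who eats a low-carbohydrate diet at baseline". But the same section also speaks of whether the intervention improves or worsens glucose tolerance, which is trial-level language.

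Section 4.4 is written for the group. For level 1: "We will test whether a fruit-rich diet can induce non-diabetic glycemia without hyperglycemia medications by testing whether our observed" rate differs from a spontaneous remission rate, given as "0.07% using an exact binomial test". Other data are analysed as change scores, with mixed models for continuous outcomes, in completers only. The percentages of participants who improve, stay the same or worsen are reported, but without a test or a decision rule. The hierarchy is not mentioned.

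**The concern.** Inside one participant the rule is sound. If that person's drugs changed, his or her glucose values are hard to read, and the change in drug need is the better evidence. At trial level the reasoning fails, because the levels then describe different people. A positive level-1 test concerns those who succeed; OGTT and CGM also carry information from people whose doses never changed and whose glucose is not confounded.

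The plan leaves both readings open, and they can lead to opposite conclusions from the same data. Section 1.1 presents the trial as able to support or refute guidance on whole fruit in type 2 diabetes. If a few successes can outrank group worsening, its ability to refute is weakened on the primary outcome. Section 5 adds a reason to settle this soon: the analysis plan was revised after some of the team had seen medication and HbA1c data from three completers.

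**Working it through.** **Inputs.** n = 16 completers ("We selected a sample size of 16 completers to provide sufficient data to inform the design of a future trial", Section 4.3). Two-sided alpha is 0.05 (Section 4.4). The null rate is 0.7% in Section 4.3 and 0.07% in Section 4.4. The alternative is 18.0% (Section 4.3). The documents give no standard deviations, so those below are assumptions.

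**1. Reproduce the stated power.** Section 4.3 says "our study has 81% power to detect an 18.0% rate of attaining non-diabetic glycemia vs. a spontaneous remission rate of 0.7"%. With rejection at 2 or more successes:

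1 − 0.82^16 − 16 × 0.18 × 0.82^15 = 1 − 0.0418 − 0.1468 = 0.811.

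This matches 81%, so 2 of 16 is the threshold behind the plan's own figure.

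**2. Smallest count that makes level 1 positive.**

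| Null | 1 of 16 | 2 of 16 |
|---|---|---|
| 0.7% | 1 − 0.993^16 = 0.106 | 1 − 0.8937 − 0.1008 = 0.0055 |
| 0.07% | 1 − 0.9993^16 = 0.011 | 0.00006 |

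Two successes suffice at 0.7%, and one at 0.07%. The exact 95% interval for 2 of 16 is 1.6% to 38.3%. If the true rate were 5% or 10% (assumed), two or more successes would occur with probability 19% or 49%.

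**3. Level 1 cannot show harm.** The lowest possible result is 0 of 16. Its probability under the null is 0.993^16 = 0.894 at 0.7%, or 0.9993^16 = 0.989 at 0.07%. Neither can be significant in the downward direction. As a test, the top level can reject only in the favourable direction.

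**4. Can the levels conflict on the analysis set the plan uses?** Lower levels are analysed in all 16, so I used all 16, with a one-sample t-test on change as a simple stand-in for the mixed model.

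*OGTT (assumed figures).* Fourteen participants on unchanged drugs rise by a mean of 15 mg/dl (SD 20), and the two achievers each change by exactly a.

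Mean m = (14 × 15 + 2a)/16

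Sum of squares = 13 × 20² + 14(15 − m)² + 2(a − m)²

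t = m/(SD/√16), on 15 df.

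| a (mg/dl) | m | SD | t | p (worsening) |
|---|---|---|---|---|
| 0 | 13.1 | 19.3 | 2.72 | 0.016 |
| −15 | 11.3 | 21.3 | 2.12 | 0.051 |
| −30 | 9.4 | 24.1 | 1.55 | 0.14 |

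*MES (assumed figures).* Two achievers fall by 1.0 and the other fourteen rise by 0.5. The mean change is (−2 + 7)/16 = 0.31, SD 0.51, t = 2.44, p = 0.028 for worsening.

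A significant whole-group worsening alongside a positive level 1 is therefore possible. For OGTT it depends on what the achievers do.

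**5. The trigger.** Sections 1.4 and 3.2 build cessation at week 10 into the design for participants who meet the glucose criterion. Read at trial level, the condition that medication doses change is met by one such medicated participant. OGTT and CGM could then be set aside for everyone, although the stated reason, confounding by dose change, applies only to the person whose dose changed.

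**The case against.** The strongest reply is that the rule was never meant for the group. It follows a definition of improvement in an individual, its rationale is confounding within a person, and its examples concern one participant. On that reading two achievers override only their own OGTT and CGM data, and everyone else is classified on their own. Section 4.4 already reports the percentages improved, unchanged and worsened. Nothing is hidden: OGTT keeps its own interpretation in Section 1.3, and HbA1c, fasting glucose and time in range are secondary outcomes. No sentence says that a positive binomial test means glycemic control improved; Section 4.4 ties that test to whether the diet can induce non-diabetic glycemia. The trial is also a single-arm pilot.

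Most of this stands, and it makes the within-participant reading the more natural one. It does not close the gap. That reading yields no primary conclusion, because the classification has no test, no decision rule and no threshold for no change. The inferential results the plan does produce are group results, and the word always in the rule carries no limit.

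A reader might go further and infer that the rule must be applied to the group, so that 2 of 16 successes would decide the trial over significant worsening in the other 14. The documents do not support that. The individual definition and examples leave the narrower reading open, and no test on the other 14 is planned. With the assumed figures such a test would give 15/(20/√14) = 2.81, p = 0.015, but it is not part of the plan; on all 16 the range is 0.016 to 0.14.

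**Conclusion.** The concern holds as a gap in specification. The unit of the hierarchy, the meaning of a positive or negative outcome, and the step from four levels to one primary conclusion are all unstated. Under the trial-level reading, which the text permits but does not favour, 2 successes (p = 0.0055 at 0.7%) or 1 success (p = 0.011 at 0.07%) would outrank a significant group worsening, and one planned cessation could set aside OGTT and CGM for all participants.

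The level-1 counts and p-values rest only on the documents' n and null rates. The conflict examples rest on assumed changes and SDs and show that conflict is possible, not how likely it is. I rate this as something that should be fixed: the more natural reading is benign, but the primary conclusion should not depend on which reading is chosen after the data are seen.

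**What to change.** In Sections 1.3 and 4.4:

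- State that supersession applies only within a participant, to classify that person as improved, unchanged or worsened, and define the no-change category at each level.
- At trial level, report all four levels side by side, with none overriding another.
- Let a significant level-1 test support only the statement that some participants can reach non-diabetic glycemia off medication.
- Prespecify how the group conclusion on glycemic control is drawn from the classification, for example improved versus worsened proportions with an exact interval or test. The choice belongs to the sponsor. A sign test is coarse at this size: 13 of 16 gives p = 0.021 and 12 of 16 gives p = 0.077. In the OGTT example, where about 11 worsen and 5 improve, it gives p = 0.21.

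The 0.7% and 0.07% null rates also need to be reconciled, since the level-1 threshold turns on which applies.

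The cost is a few sentences and one summary built on a classification the plan already intends to report. The downside is that a positive level-1 test alone no longer carries the overall claim.

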1.5 Participants

We will enroll 16 adults recently diagnosed with insulin-independent T2D. We modeled our eligibility criteria on the landmark DiRECT study, which found that a VLCD intervention induces T2D remission in 46% of patients [3]. Like the DiRECT study, we are recruiting adults with insulin-independent T2D who were diagnosed with T2D within the past six years, as patients with diabetes durations longer than 6–8 years are less likely to achieve remission.² Table S1 in the appendix shows the eligibility criteria. To be eligible, applicants must have an HbA1c between 6.0–9.5%, be aged 20–70 years, and have a body mass index (BMI) \leq 45.0 kg/m². Key exclusion criteria include an estimated glomerular filtration rate (eGFR) <45 ml/min per 1.732 m², a change in body weight >5 kg in the past six months, a change in a chronic medication dosage that may affect study endpoints within the past three months, a significant health condition that might compromise the participant's safety or data validity, or inability to follow the study protocol. All participants must provide written informed consent prior to enrolling in the study. Participants are provided with a stipend, food, and a high-speed blender as compensation.

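### Section 1.3 reads a CGM change as only an acute diet effect when assessments 1-3 show no change, but the plan has no criterion for no change and a non-significant OGTT at n=16 cannot exclude a medium effect

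*Combined protocol and SAP*

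**What the plan says.** Section 1.3 ranks four glycemic assessments: (1) non-diabetic glycemia off medication, (2) the medication effect score (MES), (3) mean glucose in the three-hour OGTT, and (4) mean 24-hour CGM glucose adjusted by the MES. Findings at a higher level override those below. For the case without medication changes it says: "If there are no changes in glucose-lowering medications, then we will use assessments 3 and 4 to determine whether there are changes in glycemic control". It then gives the rule at issue: "If there is no change in assessments 1-3, we will interpret assessment 4 (CGM) to reflect only acute changes in the glycemic load" and the macronutrient composition of the diet. Two examples follow, each about a single participant and each worded with *may*.

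Section 4.3 says "We selected a sample size of 16 completers to provide sufficient data to inform the design of a future trial" and that "16 completers provides 80% power to detect effect sizes of" d = 0.78 or more with a two-tailed paired t-test. It adds: "We acknowledge that we are not powered to detect medium or small effect sizes, which may also be clinically relevant". Section 4.4 says "All statistical tests will be two-sided with a Type I error rate of" 0.05 and "we will analyze the data per protocol in completers only", with week 0 versus week 12 as the primary comparison. Continuous outcomes are tested for differences in linear mixed models. Section 4.4 also promises the percentages of participants who improve, stay the same or worsen. Neither there nor in Section 1.3 is there a margin, a minimal important difference or an interval criterion for no change.

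**The concern.** The rule draws a positive causal conclusion, that the CGM shift is dietary and nothing more, from the absence of a detected change higher up. At group level, the only way the plan offers to find no change is a difference test that fails to reach 0.05. Section 4.3 concedes that such tests can miss effects that matter clinically, but Section 1.3 does not carry that limit into its rule. A CGM change accompanied by a real but undetected OGTT change, in either direction, would be attributed to acute diet effects alone. That attribution concerns a component of the primary outcome, and it bears on the trial's central question of whether the diet changes glucose metabolism.

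**Working it through.** **Inputs.** From the plan: 16 completers (Section 4.3), two-sided alpha 0.05 and the week 0 to 12 contrast (Section 4.4), paired t-test (Section 4.3). Assumed: medium means d = 0.5 on the SD of the paired change, since Section 4.3 gives no number; the range 0.3 to 0.6 is shown.

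**Formula.** Paired t-test power = P(|T| > t(0.975, n−1)), where T is noncentral t with n−1 degrees of freedom and noncentrality d√n. At n = 16 the critical value is t(0.975, 15) = 2.131 and √n = 4.

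**The plan's own figure.** At d = 0.78 and n = 16, power is 83.0%. The d that gives exactly 80% is 0.75, and n = 15 gives 80.2% at d = 0.78. The stated 80% is therefore slightly conservative but consistent with this formula and this scale for d.

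**Chance of a non-significant OGTT at n = 16** (1 − power):

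| True d | Power | Non-significant |
|---|---|---|
| 0.3 | 20.3% | 79.7% |
| 0.4 | 32.2% | 67.8% |
| 0.5 | 46.5% | 53.5% |
| 0.6 | 61.2% | 38.8% |

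**Sensitivity at d = 0.5.**
- Mixed model with three timepoints: residual degrees of freedom (16−1)×(3−1) = 30, power 49.0%, miss rate 51.0%.
- Dropout: Section 1.5 says "We will enroll 16 adults recently diagnosed with insulin-independent T2D", while Section 4.3 counts 16 completers. The miss rate is 59.0% with 14 completers and 64.7% with 12.
- If d = 0.5 were on the raw SD, then d on the change scale is 0.5/√(2(1−r)), with r the within-person correlation. Power is 35.3% at r = 0.3, 46.5% at r = 0.5 and 67.5% at r = 0.7.

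**What a non-significant result excludes.** The 95% interval half-width is 2.131/4 = 0.533 SD of the observed change. A non-significant result has zero inside the interval, so the interval reaches at least 0.533 SD from zero on one side. It therefore always contains +0.5 SD or −0.5 SD, and often both.

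**How often the whole rule fires.** It needs no change in assessments 1, 2 and 3 together, so 53.5% applies only when 1 and 2 are unchanged. Section 4.4 treats one case of non-diabetic glycemia off medication as showing a non-zero rate, so on that reading assessment 1 is unchanged only with 0 cases in 16. Assuming independence and a true OGTT effect of d = 0.5:
- true rate 5%: 0.535 × 0.95^16 = 0.535 × 0.440 = 24%
- true rate 10%: 0.535 × 0.90^16 = 0.535 × 0.185 = 10%
- true rate 18% (the rate used in Section 4.3): 0.535 × 0.82^16 = 0.535 × 0.042 = 2%

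**What a margin rule would deliver.** By simulation at n = 16 with a true OGTT change of zero, the 95% interval lies inside ±0.5 SD about 8% of the time and inside ±0.78 SD about 66%.

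**The case against.** **The rule may be meant for individuals.** Section 1.3 defines improvement for an individual, both of its examples concern one participant, and Section 4.4 reports participant percentages. This stands: equating no change with non-significance is an inference, and no t-test figure applies at participant level. The gap remains, because the plan gives no threshold for calling one person's OGTT unchanged.

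**The rule will fire less often than half the time.** This also stands. A reader might take 53.5% as the overall frequency of the error. It is conditional on assessments 1 and 2 being unchanged, and the working shows how quickly the joint frequency falls when assessment 1 responds. The condition is nevertheless the branch in which Section 1.3 lets assessments 3 and 4 decide.

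**A mislabelling rate.** One might simulate a significant CGM change with a non-significant OGTT. With an OGTT effect of 0.5, a CGM effect of 0.75 and correlation 0.5 this happens 38% of the time (50% if the OGTT effect is 0.4). It falls to 17% when both effects are 0.5 and to 15% when both are 0.4. None of these inputs is in the documents. Nor would the result show mislabelling, since a CGM effect larger than the OGTT effect is also what an acute diet contribution would produce.

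**Hidden harm.** A reader might infer that the rule conceals worsening. The documents do not support that. CGM is still reported, and HbA1c, fasting glucose, insulin sensitivity, insulin secretion and time in range are separate outcomes (Section 1.3). Worsening is tabulated (Section 4.4), and CGM data are reviewed at least twice a week for safety (Section 1.9). The fault lies in interpretation.

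**It is a pilot, and it admits low power.** True, but the admission in Section 4.3 does not repair a rule in Section 1.3 that needs adequate power to be sound.

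**Conclusion.** The point holds in a conditional form. The plan attaches an *only acute* conclusion to an undefined finding of no change. Read at group level, with assessments 1 and 2 unchanged and 16 completers, a true OGTT effect of d = 0.5 goes undetected 53.5% of the time (79.7% at d = 0.3, 38.8% at d = 0.6). No non-significant OGTT result can exclude a half-SD effect in both directions. The size rests on three assumptions: the value taken for medium, the paired-change scale for d, and the group-level reading. It is not an estimate of how often the trial will reach a wrong conclusion, and it does not show that CGM changes will be mislabelled. It shows that the stated inference is unsupported when the rule applies. The point is worth correcting before analysis, and a change of wording is enough.

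**What to change.** In Section 1.3, replace the *only acute* wording. Say that a CGM change without a detected change in assessments 1-3 may reflect acute diet effects but that its cause is not determined. Report the week 0 to 12 change in OGTT mean glucose with its 95% confidence interval beside the CGM result.

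Keep the stronger conclusion, acute diet effect only, solely for the case where that interval lies inside a margin that the sponsor fixes and justifies in advance. State that the rule applies at group level.

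The cost is a few sentences of SAP text and, if the stronger label is kept, one margin; no further data or participants are needed. The downside is that not determined will be a common answer at this sample size. Even with no true OGTT change, a ±0.5 SD margin would be met about 8% of the time and a ±0.78 SD margin about 66%. These two margins only illustrate the cost and are not proposals.
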